#### 10.5 Discontinuation/Withdrawal of Participants from Study Treatment

Participants may be withdrawn from treatment, or from the study as a whole; if they ask to withdraw, if participant safety is in question or if the study is stopped early.

#### 10.6 Definition of End of Study

The end of study will be the date of the last visit of the last participant.

## 11. INTERVENTIONS

### 11.1 Description of Study Intervention / Treatment

10 days of moderate home-based overnight normobaric hypoxia ( $F_{I}O_2 = \sim 0.155$ , or sham hypoxia intervention ( $F_{I}O_2 = 0.2093$ ) using hypoxic 'pillow tents'.

### 11.2 Adherence to Study Treatment

Participants will be asked to confirm compliance and complete a diary confirming the exposure.  $SpO_2$  will be recorded and used as confirmation.

### 11.3 Accountability of the Study Treatment

Ultimately, the chief investigator ([name]) is responsible for all aspects of the study. However, the appointed post-doctoral researcher will be responsible for installing the hypoxic generators and monitoring adherence.

### 11.4 Concomitant Medication / Therapies

Participant involvement is anticipated to be ~2 months. Medication will be recorded on enrolment and updated throughout their time in the study.

## 12. ASSESSMENT OF SAFETY (IF APPLICABLE)

A serious adverse event is any untoward medical occurrence that:

- Results in death,
- Is life-threatening,

NOTE: The term "life-threatening" in the definition of "serious" refers to an event in which the participant was at risk of death at the time of the event; it does not refer to an event which hypothetically might have caused death if it were more severe.

- Requires inpatient hospitalisation or prolongation of existing hospitalisation,
- Results in persistent or significant disability/incapacity, or
- Is a congenital anomaly/birth defect.
- Other important medical events\*

\*Other events that may not result in death, are not life threatening, or do not require hospitalisation, may be considered a serious adverse event when, based upon appropriate medical judgement, the event may jeopardise the participant and may require medical or surgical intervention to prevent one of the outcomes listed above.

### 12.2 Reporting Procedures for Serious Adverse Events

A serious adverse event (SAE) occurring to participant should be reported to the REC that gave a favourable opinion of the study where in the opinion of the Chief Investigator the event was: 'related' – that is, it resulted from administration of any of the research procedures; and 'unexpected' – that is, the type of event is not listed in the protocol as an expected occurrence. Reports of related and unexpected SAEs should be submitted within 15 days of the Chief Investigator becoming aware of the event, using the NRES [report of serious adverse event](#) form (see NRES website).

### 12.3 Recording and Reporting Procedures for All Adverse Events

All adverse events will be recorded in participant file notes. Distinction between SAE and AE will be made by an independent medical officer. All SAE will be reported to the sponsor and the REC regardless of if it is related or not.

### **13. DATA HANDLING AND RECORD KEEPING**

#### **13.1 Data Collection Forms**

Visit 1 will act as a consent, screening and hypoxic screening to allow for medical clearance. All data for these visits will be stored in the clinical record folder (CRF). Separate forms will be prepared for; anthropometrics, medical history, screening (i.e. blood pressures etc) and blood markers. All paper copies will be stored in the CRF's.

#### **13.2 Data Management**

All study data (excluding electronic files) will be entered on paper copies and stored in participant CRF's. Electronic files will be stored on a shared (with access restricted to only the research team) google drive. All data will be double data entered into excel. Macro's will be used to check for anomalies and corrected. The participants will be identified by a study specific participants number and/or code in any database. The name and any other identifying detail will NOT be included in any study data electronic file. The chief investigator ([name]) is responsible for database maintenance and management.

## 14. DATA ANALYSIS

### 14.1 Description of Analysis Populations

All participants who complete all visits will be entered into the analysis as per protocol.

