Study Design	Single blind, randomized, balanced, crossover design study (i.e. participants will undergo both the hypoxia and sham conditions and will be blinded to the conditions in which they are in).
Study Participants	Individuals with type 2 diabetes
Planned Sample Size	The study of 23 subjects provides adequate power (including a 15% drop-out rate typically seen in our clinical trials): 13 subjects are required to detect a 1 standard deviation change [30] in venous blood [glucose] during a 2 hour oral glucose tolerance test (OGTT (alpha = 0.05; power = 80%)).
Follow-up duration	1 months washout – 10 day intervention
Planned Study Period	1 year
Primary Objective	Post-intervention (sham vs hypoxia) area under curve for venous blood [glucose] during a 2 hour OGTT.
Secondary Objectives	Fasting venous blood [glucose], peak venous blood [glucose] during OGTT, Homeostatic Model Assessment for Insulin Resistance (HOMA-IR), daily glucose excursions (continuous glucose monitoring), and untargeted metabolomics, body mass / composition change, hormonal markers of appetite (e.g. leptin and ghrelin), food intake, gut microbiome, markers of inflammatory status (e.g. interleukin-6; nitrite), redox balance (TNF $\alpha$ ; SOD), HIF-1 $\alpha$ , extracellular HSP70, physical activity and sleep quality.
Primary Endpoint	Post-intervention (sham vs hypoxia) area under curve for venous blood [glucose] during a 2 hour OGTT.
Secondary Endpoints	See secondary objectives.
Intervention (s)	10 days of moderate home-based overnight normobaric hypoxia (F 1 O 2 = ~0.155, or sham hypoxia intervention (F 1 O 2 = 0.2093) using hypoxic ‘pillow tents’.

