## 7. STUDY DESIGN

### 7.1 Summary of Study Design

Single blind, randomized, balanced, crossover design study (i.e. participants will undergo both the hypoxia and sham conditions and will be blinded to the conditions in which they are in).

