### *Intervention*

[figure not shown]
Participants will undertake 10 days of moderate home-based overnight normobaric hypoxia (FIO2 = ~0.155), and a sham hypoxia intervention (FIO2 = 0.2093) using hypoxic 'pillow tents' in a random order. The use of pillow tents rather than whole body tents was based on patient and public involvement (PPI) consultations. Participants will wear an SpO2 monitor at all times within the tent that will sound an alarm if SpO2 falls too low. If it sounds, participants will remove the hood (so that they breathe ambient air) and leave it off for the remainder of the night. An independent medical officer will decide if the participants can remain in the trial. The O2 fraction will be set by the researcher and participants instructed not to change the settings. Finally participants will be asked to maintain a diary of the time spent in the tent. Finally, participants will be asked to record a dietary diary and photograph meals in order to try and replicate it in both conditions. Participants will then undertake the alternative condition. The cross-over conditions will be separated by a minimum 4 week wash out period. During the intervention, as well as recording safety information (ie. SpO2) we will ask participants to wear a continuous glucose monitor (CGM) sensor (Abbott Diabetes Care Inc., Alameda, CA, USA) on the anterior portion of the upper arm with a small adhesive patch. These sensors will be worn for 14 days to determine free-living glycaemic control, in addition to a wrist-worn accelerometer (GENEActiv, Activinsights, Kimbolton, Cambridge, UK) to assess baseline habitual physical activity (PA) and sleep [32] (see details below in section 10.4).

*Visit 2, 3, 4 and 5 (approx 2.5 per visit)*

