### 14.2 Analysis of Endpoints

All data will be tested for normality using the Shapiro-Wilk test. For normally distributed data, paired samples t-tests will be used to assess differences pre and post hypoxic exposures for; blood [glucose] (AUC and peak), insulin sensitivity, eHSP70, IL-6, leptin, ghrelin, TNFa, SOD, HIF-1 $\alpha$  HR, PA and sleep efficiency. For non-parametric data Wilcoxon-Signed rank test will be used for pairwise comparisons. Repeated measures one-way analysis of variance (ANOVA) will be used to identify differences between conditions for SpO2 and [glucose] across time from the CGMs. Mauchly's test of sphericity will be used to determine if any data violated the assumption of spherical data. If violated, sphericity will be accounted for using the Greenhouse-Geisser correction. Where significant differences are observed ( $P < 0.05$ ), post-hoc tests will be performed using LSD pairwise comparisons. Effect sizes will be reported as partial eta squared ( $\eta^2_p$ ) (small = 0.01; medium = 0.06; large = 0.14) [33].

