### 14.3 Procedure for Dealing with Missing, Unused and Spurious Data

Outliers will remain within the data. Within the data analysis software missing data will be coded 9999 and the data point missed during analysis.

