### 14.4 Procedures for Reporting any Deviation(s) from the Original Statistical Analysis Plan

For this pilot a SAP is not required (excluding the above).

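### The only analysis set is participants who attend every visit, which discards usable primary-endpoint data and can bias the estimate in either direction

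*Combined protocol and SAP*

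**What the plan says.** The trial is a "Single blind, randomized, balanced, crossover design study" of hypoxia against sham. The primary endpoint (sections 2 and 7.2) compares the glucose AUC after each condition. Section 10 makes visits 2 and 4 the baselines and visits 3 and 5 the post-exposure assessments.

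Section 14.1 names one analysis population: "All participants who complete all visits will be entered into the analysis as per protocol". The last three words may label a per-protocol set or may simply mean according to the protocol. Either way, no second set is given. On missing values, section 14.3 says only that "missing data will be coded 9999 and the data point missed during analysis". Section 14.4 closes off a further document: "For this pilot a SAP is not required (excluding the above").

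Losses are expected. The synopsis sizes the trial "including a 15% drop-out rate typically seen in our clinical trials". Two routes out are described. After a low-saturation alarm, "An independent medical officer will decide if the participants can remain in the trial" (section 10, Intervention). Section 10.5 adds that "Participants may be withdrawn from treatment, or from the study as a whole", on request, for safety, or if the study stops early.

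**The concern.** Attendance at every visit is a stricter condition than the primary endpoint needs. That endpoint uses visits 3 and 5, yet missing a baseline removes a participant altogether. A participant who completes one period and then leaves also contributes nothing, although the first post-intervention OGTT carries information about the condition effect.

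There is also a question of bias. A completers-only contrast is safe when leaving is unrelated to outcome. If people leave partly because of what happened in period 1, those who remain are a selected group. Section 20 says the effect sizes and confidence intervals will be used to power a definitive trial, so a distorted estimate would carry forward into that design.

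**Working it through.** **1. Expected loss.** The synopsis gives 23 recruited, 15% drop-out and 13 required. Expected loss is 23 × 0.15 = 3.45 and expected completers 23 × 0.85 = 19.55, well above 13. The issue is therefore which data are used and possible bias, not a shortage of completers. (13/0.85 = 15.3, so 16 would cover the stated drop-out; that neither 23 nor the 20 in section 9 follows from it is a separate matter.)

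**2. Who is discarded.**

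| Visits attended after visit 1 | Post-intervention OGTTs held | In the section 14.1 set? |
|---|---|---|
| 2, 3, 4, 5 | both | yes |
| 2, 3, 5 | both | no |
| 3, 4, 5 | both | no |
| 2, 3, then left | one | no |
| left before 3 | none | no |

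Rows two and three hold the complete primary endpoint. Row four holds half of it. Section 14.2 words its test differently ("paired samples t-tests will be used to assess differences pre and post hypoxic exposures for" the listed outcomes). On that wording, a participant in row four who had hypoxia first holds everything the test needs and is still dropped.

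**3. Possible scale of missed visits.** The documents give no miss rate per visit. Assuming 5%, independent between visits:
- all four assessment visits required: 1 − 0.95⁴ = 0.185, about 19% lost;
- the two post-intervention visits only: 1 − 0.95² = 0.0975, about 10% lost.

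**4. Bias.** Illustrative simulation with 23 participants in two sequences, 4 lost after period 1 (4/23 = 17%), true effect −0.5 SD, and total SD of a single AUC set to 1. The within-person correlation ρ is not given, so 0.5 to 0.85 is assumed. Completers are analysed by a period-adjusted paired contrast. The alternative is a linear mixed model with condition and period fixed and participant random, on all post-intervention values.

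| Who leaves | Completers, ρ = 0.5 | Completers, ρ = 0.85 | All-data model |
|---|---|---|---|
| Hypoxia-first participants with high post-hypoxia glucose | about −0.62 | about −0.55 | about −0.50 |
| Either sequence, high period-1 glucose | about −0.46 | about −0.49 | about −0.50 |
| At random | about −0.50 | about −0.50 | about −0.50 |

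The completers' standard error is roughly √(2(1 − ρ)/19): 0.23, 0.18 and 0.13 at ρ = 0.5, 0.7 and 0.85. The simulated values were 0.22, 0.18 and 0.13, and the all-data model's were essentially the same.

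**5. Size against noise.** At ρ = 0.5 the largest overstatement is 0.62 − 0.50 = 0.12 SD, or 0.12/0.22 = 0.55 of a standard error. The largest understatement is 0.50 − 0.46 = 0.04 SD, or 0.18 of a standard error.

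**The case against.** A reader might infer that the rule drops people who do not respond to hypoxia. The documents do not support this. Section 10.5 does not list non-response as a reason for withdrawal, participants are blinded to condition, and a non-responder who attends every visit is analysed.

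A reader might also infer that the result describes only people who tolerate the tent. That too goes beyond the text. Section 14.1 selects on attendance, not adherence, and section 11.2 sets no adherence threshold. After an alarm the hood stays off for that night, and continuation is decided case by case. Someone who scarcely uses the tent but attends every visit stays in the set and dilutes the effect.

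The strongest inference would be that a completers-only estimate must flatter hypoxia. The overstatement above needs loss concentrated in the hypoxia-first sequence. Four losses from a sequence of 11 or 12 is about a third of it, and nothing in the documents predicts that pattern. Loss after high period-1 glucose in either sequence understates the effect.

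The remedy has a limit as well. Suppose 15% cannot tolerate hypoxia, gain nothing and have no post-hypoxia OGTT, while the rest gain 1 SD. The average over all randomised is 0.85 × 1 + 0.15 × 0 = 0.85 SD, but completers and the mixed model both return 1.00, because the model assumes that leavers would have responded like stayers. Only attendance after stopping the tent closes that gap.

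Finally, this is a pilot, and the simulated biases are smaller than one standard error. That limits the urgency. It does not justify discarding complete endpoint data. Nor does section 14.3 rescue those data: it covers missing values among participants analysed, whereas section 14.1 decides who is analysed.

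**Conclusion.** The concern stands in this form: all-visit completers are the sole analysis set, the rule discards participants who hold part or all of the primary endpoint, and the estimate can be biased if leaving depends on the observed period-1 result. The direction is not established. In the scenarios tried, the completers' estimate ran from about −0.62 to about −0.46 against a true −0.50, while the all-data model stayed at about −0.50 with no material loss of precision.

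These figures rest on an assumed within-person correlation, 4 losses in 23 and assumed drop-out patterns. They show what could happen and do not forecast this trial. The 19% against 10% comparison rests on an assumed 5% miss rate per visit. That data are discarded needs no assumption beyond section 14.1 being followed as written.

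**What to change.** In section 14.1:
- Define the primary set as all randomised participants with at least one post-intervention OGTT, analysed by allocated condition in a linear mixed model with condition and period as fixed effects and participant as a random effect.
- Keep the all-visit completers as a sensitivity analysis.

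In sections 10.5 and 14:
- Invite participants who stop treatment but remain in the study, a category that section 10.5 already allows, to attend the visits already scheduled for them.
- Report withdrawals by condition, period and reason, so that readers can judge whether loss was related to hypoxia.
- State that the mixed model handles loss related to observed results and does not correct loss driven by unobserved post-hypoxia values.

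The cost is plan wording and slightly more analysis work, with no new visits or procedures. The estimate may turn out less favourable than the completers' one.

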### 14.2 Analysis of Endpoints

All data will be tested for normality using the Shapiro-Wilk test. For normally distributed data, paired samples t-tests will be used to assess differences pre and post hypoxic exposures for; blood [glucose] (AUC and peak), insulin sensitivity, eHSP70, IL-6, leptin, ghrelin, TNFa, SOD, HIF-1 $\alpha$  HR, PA and sleep efficiency. For non-parametric data Wilcoxon-Signed rank test will be used for pairwise comparisons. Repeated measures one-way analysis of variance (ANOVA) will be used to identify differences between conditions for SpO2 and [glucose] across time from the CGMs. Mauchly's test of sphericity will be used to determine if any data violated the assumption of spherical data. If violated, sphericity will be accounted for using the Greenhouse-Geisser correction. Where significant differences are observed ( $P < 0.05$ ), post-hoc tests will be performed using LSD pairwise comparisons. Effect sizes will be reported as partial eta squared ( $\eta^2_p$ ) (small = 0.01; medium = 0.06; large = 0.14) [33].

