### *Hypoxic screening and familiarisation*

Participants will be assessed for lung function (FVC and FEV1/FVC ratio, PEF). Participants will undergo a one hour, supine exposure to hypoxia (FIO2 = ~0.155, adjusted based upon oxyhaemoglobin saturation during pilot hypoxic exposure to ensure target SpO2 of ~88-92 %). Participants' desaturation will be recorded. Anyone who desaturates to below 65 % SpO2 or in whom end tidal CO2 or O2 of less than 25 mmHg or 45 mmHg respectfully is recorded. Eligible participants will then be randomly allocated (using randomizer.org) to start in either the hypoxia or sham condition (see details below). Participants will be sent home with a SpO2 (Equivital EQ02, Hidalgo, UK) monitor that will record oxygen saturation for 2 nights so that we can screen for undiagnosed sleep apnoea. Finally, a time will be scheduled within the next two days to set up the hypoxic generator, and the hood at the participant's home.

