Visits 2-5 are identical in nature. Visits 2 and 4 are baseline visits before each arm of the crossover (i.e. the intervention). Visits 3 and 5 are following the 10 day hypoxic or sham exposures to assess the outcomes. An OGTT, body composition and venous blood samples and a stool collection will occur on each visit. After visit 3 there will be a 4 week washout out period. Visit 4 is necessary to ensure participants are back to baseline. During this visit, if anyone has had a respiratory tract infection or infectious disease in between visits, the hypoxic screening and lung function tests will be repeated. During visit 3, a new CGM sensor will be secured and accelerometer worn and a home visit for set-up will be re-booked. At the end of visit 5, another CGM and accelerometer will be affixed to the participants to check how long the effects of the intervention take to decay.

Urine collection is critical for our metabolomics analysis. In order to look for trends across time and between conditions we will need to collect urine before, during and after the intervention. Participants will be asked to collect a small urine sample for 2 days before the intervention starts, for each day of the intervention and for 2 days following the intervention. Participants will be provided with instructions on how to collect a mid-flow urine sample and how to safely store the samples until they are collected.

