### **Oxygen saturation**

An SpO2 monitor (Equivital EQ02, Hidalgo, UK) will be set up at the participant's home. Participants will wear the monitor at all times during exposure to hypoxia. If saturation falls below (65%) an alarm will be sounded. This system also records beat to beat heart rate and will store the data on the device until it is collected. Participants will also be asked to maintain a diary of the time spent in the tent.

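### Section 14.2 tests heart rate before versus after hypoxia, but the prose describes no heart-rate recording after exposure; the in-tent hypoxia-versus-sham comparison should be specified instead (minor).

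*Combined protocol and SAP*

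**What the plan says.** Section 14.2 states that "paired samples t-tests will be used to assess differences pre and post hypoxic exposures for" a list of variables ending in "HR, PA and sleep efficiency", with a signed-rank test where normality fails. HR is not in the abbreviations list; heart rate is the natural reading.

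The recorder is described under Oxygen saturation in 10.4: "This system also records beat to beat heart rate and will store the data on the device until it is collected". Its wear times are given in three places:

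- Section 10, Hypoxic screening and familiarisation: participants go home after visit 1 with a "monitor that will record oxygen saturation for 2 nights so that we can screen for undiagnosed sleep apnoea".
- Section 10, Intervention: they wear an SpO2 "monitor at all times within the tent that will sound an alarm" if saturation drops too far.
- Section 10.4, Oxygen saturation: "Participants will wear the monitor at all times during exposure to hypoxia".

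For the four visits that bracket the two conditions, Section 10 says: "An OGTT, body composition and venous blood samples and a stool collection will occur on each visit". After visit 5, "another CGM and accelerometer will be affixed to the participants to check how long the effects of the intervention take to decay". A 12-lead ECG is done at visit 1. The key to the participant-flow chart lists heart rate variability and oxygen saturation among the assessments.

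**The concern.** A paired pre/post test needs one value before and one value after the exposure. The schedule described for the heart-rate recorder is built around safety monitoring during exposure, plus an apnoea check at entry. It does not obviously supply the second value, or a fresh first value for the second condition.

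Section 14.4 says that no further analysis plan is required, so 14.2 is all the analyst has. Followed as written, it leaves the meaning of pre and post to be settled once the data are in. Home nights against tent nights, first tent night against last, or some other pairing would each answer a different question. A before/after comparison within hypoxia also leaves out the sham condition, which is what the crossover was designed to provide.

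**Working it through.** The plan gives no figure to reproduce here. The check is a count of heart-rate recordings described in the prose, followed by a look at what each candidate contrast estimates.

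**1. Recordings described**

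| Point in the trial | Heart-rate recording in the prose | Where |
|---|---|---|
| Visit 1 | one 12-lead ECG | Section 10, consent and screening |
| Home, after visit 1 | 2 nights | Section 10, Hypoxic screening |
| Visit 2 (before condition 1) | none described | Section 10, Intervention |
| Condition 1 | up to 10 tent nights | Sections 10 and 10.4 |
| Visit 3 (after condition 1) | none described | Section 10, Intervention |
| Visit 4 (before condition 2) | none routinely; the hypoxia test and spirometry are repeated only after an infection, with no further home nights stated | Section 10, Intervention |
| Condition 2 | up to 10 tent nights | Sections 10 and 10.4 |
| Visit 5 and after | none described; glucose sensor and accelerometer only | Section 10, Intervention |

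The prose therefore describes 0 of 2 post-exposure values and 1 of 2 period baselines. Ten tent nights is a planned maximum, because after an alarm the hood stays off for the rest of that night.

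**2. If the 2 home nights are taken as the pre value**

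- Hypoxia-first participants: the home nights come shortly before the hypoxia.
- Sham-first participants (about half in a balanced design): the sham condition and the washout come between. Minimum gap = 10 days + (4 weeks × 7) = 10 + 28 = 38 days.

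The baseline therefore means something different in the two sequences.

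**3. What each contrast estimates**

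- Hypoxia tent nights minus home nights = effect of hypoxia + effect of sleeping in the tent + change over time.
- Any later post-hypoxia value minus a pre value = after-effect of hypoxia + after-effect of the tent routine + change over time.
- Hypoxia tent nights minus sham tent nights, within person = effect of hypoxia during exposure + period difference. The tent effect cancels, and the balanced order offsets the period difference.

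Only the third uses the sham control, and it needs no recording beyond tent nights in both conditions.

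**4. Comparison with SpO2**

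Section 14.2 already analyses SpO2, from the same device on the same nights, between conditions. HR is the one output of that device placed in the pre/post list.

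**5. Are sham nights recorded?**

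The Intervention text ties wear to being in the tent, which covers sham. The 10.4 text ties it to hypoxic exposure, which read literally does not. The between-condition contrast depends on the first reading.

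**The case against.** The strongest objection is that the schedule cannot be judged from the prose alone. The flow-chart key lists HRV and SPO2, HRV is mentioned nowhere else in the text, and the contents list names a schedule of procedures and a flow chart that were not available. A reader might infer from the prose that no post-exposure heart rate will exist and that the test cannot be run. The documents do not support that: the chart may place recordings at the pre and post visits. This part of the objection stands, so the count above describes the prose only.

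A reader might also infer that the second condition can have no pre value. That assumes a separate baseline for each period. Section 14.2 does not require one, and the home nights could serve as a single common baseline. The plan does not say so, and that baseline would be weak for sham-first participants, but it would not be absent. Nor should the home nights be taken as preceding randomisation: Section 10 mentions allocation before the monitor is sent home. They are best called pre-exposure.

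It is also fair to say that the pre/post wording in 14.2 covers other outcomes, including glucose AUC, and that rewriting the whole sentence as hypoxia versus sham would take in HR. That is true. HR still needs its own line, because the other outcomes taken from the OGTT and blood samples have described measurements before and after each condition, and HR does not.

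None of this rescues the planned contrast. Even if the chart shows pre and post recordings, a comparison within hypoxia alone ignores the sham condition.

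**Conclusion.** The point holds as a minor one. On the prose, the HR test in 14.2 does not match the heart-rate recording described in Sections 10 and 10.4: no post-exposure recording and no routine recording before the second condition is described. Whether the flow chart fills those gaps has to be confirmed against the chart. Independently of that, the planned contrast does not use the sham control.

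The consequence is small. HR appears in neither the primary nor the secondary outcomes in 7.2, no stated hypothesis depends on it, and the primary result and sample size are unaffected. A reader might take this as a defect in the trial's main comparison; the documents give no ground for that.

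The conclusion assumes that HR means heart rate, that the Equivital is its intended source, and that the monitor is worn on sham nights as the Intervention text indicates.

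**What to change.** In 14.2, take HR out of the pre/post list. State that each participant's mean in-tent overnight heart rate will be compared between hypoxia and sham, paired within person, over the nights actually recorded, in line with the between-condition analysis already planned for SpO2. Use the 2 home nights for description only.

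In 10.4, reconcile the two statements of when the monitor is worn, so that it is clear whether sham nights are covered. Check the flow chart. If it schedules HRV or heart-rate recordings at other times, state those times in 10.4.

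The cost is one sentence in 14.2 and a short clarification in 10.4. No new data are needed, provided the monitor is worn on sham nights.

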### **Continuous glucose monitoring (CGM)**

The sensors (Abbott Diabetes Care Inc., Alameda, CA, USA) will be fixed to the anterior portion of the upper arm with a small adhesive patch. These sensors will be worn for 14 days to determine free-living glycaemic control.

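### The one-way repeated-measures ANOVA for SpO2 and CGM glucose does not define its factor; if time levels enter it, a significant F is not a test of hypoxia against sham, and the LSD follow-up loses its protection

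*Combined protocol and SAP*

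**What the plan says.** Section 7.1 sets out a crossover in which "participants will undergo both the hypoxia and sham conditions". Section 10 gives 10 nights of exposure per condition with SpO2 recorded. Of the CGM sensors, section 10.4 says: "These sensors will be worn for 14 days to determine free-living glycaemic control".

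For these two series section 14.2 states: "Repeated measures one-way analysis of variance (ANOVA) will be used to identify differences between conditions". The outcomes are SpO2 and "glucose] across time from the CGMs". It continues: "Mauchly's test of sphericity will be used to determine if any data violated the assumption of spherical data". If it is violated, "sphericity will be accounted for using the Greenhouse-Geisser correction". When the result passes P < 0.05, "post-hoc tests will be performed using LSD pairwise comparisons". Effect sizes are to be reported as partial eta squared, with 0.01, 0.06 and 0.14 as small, medium and large.

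The plan does not state how many time levels enter the model, whether the single factor is condition, time or their combination, or which contrast answers the question. It has no condition-by-time or period term. Section 14.4 says no further SAP is required, so no other text settles this. The only multiplicity correction in the protocol is Benjamini-Hochberg for microbiome taxa (section 10.4).

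**The concern.** A one-way model has one factor; these data have two, condition and time, both within person. What the F test means depends on which one is used.

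- **Condition, one summary per person per condition.** With two levels this is a paired t-test and is valid. But with two levels the sphericity test, the Greenhouse-Geisser correction and the post-hoc comparisons have nothing to do, and the comparison across time disappears.
- **Time, within each condition.** Hypoxia is never compared with sham.
- **Condition-by-time cells.** F mixes the condition effect, the time effect and their interaction. A drift over nights that is the same in both conditions can make it significant.

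The reference to time and the sphericity and post-hoc steps point to more than two levels, so the second or third reading is the more natural one. On the third, LSD relies on a gate that a time trend alone can open. After that each pairwise test runs at 0.05.

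What is at stake is mainly CGM glucose, a listed secondary outcome and the trial's free-living measure of glucose control. Section 20 says that effect sizes from this pilot will be used to choose the primary outcome of the definitive trial and to power it.

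**Working it through.** The documents give no error rate or power for this analysis, so there is no stated figure to reproduce.

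**Inputs from the protocol.** Two conditions per person (7.1). Ten nights per condition, and 14 days per CGM sensor (10, 10.4). Gate P < 0.05 (14.2). N = 23 with 15% drop-out (synopsis): 23 × 0.85 = 19.55, taken as 19 completers.

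**Assumptions.** Ten analysed time levels per condition; residual SD 1; independent residuals; a participant effect; a linear trend shared by both conditions, its size given as the SD of the night means in residual SDs; two-sided tests.

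**Number of comparisons.** 2 × 10 = 20 cells give 20 × 19 / 2 = 190 pairs. With 14 days, 28 cells give 28 × 27 / 2 = 378. For same-night hypoxia-sham pairs alone, if the gate is always open and the tests are independent, the chance of at least one false positive is 1 − 0.95^10 = 0.40, or 1 − 0.95^14 = 0.51.

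**Simulated error with no condition effect.** The one-way F is computed on the 20 cells. If it is significant, unadjusted paired tests are run for each night. Figures in brackets apply Greenhouse-Geisser.

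| Shared trend SD | One-way F rejects | At least one false same-night LSD difference | Condition main effect rejects |
|---|---|---|---|
| 0 | 6% (1%) | 5% (1%) | about 5% |
| 0.1 | 14% (5%) | 10% (3%) | about 5% |
| 0.2 | 62% (38%) | 30% (20%) | about 5% |
| 0.3 | 96% (90%) | 39% (38%) | about 5% |

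Repeat runs agree to within about two percentage points.

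**Number of time levels.** With a larger time effect (amplitude one residual SD), 13 or 19 completers and Greenhouse-Geisser applied, the chance of a false matched-time LSD difference is 0.08–0.10 for 2 time levels, 0.14 for 3, 0.37–0.40 for 10 and 0.48–0.51 for 14. Bonferroni-adjusted matched-time tests bring this to about 0.04–0.06.

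**Power for a true 0.5 SD condition effect, no trend, 19 completers, 10 nights.** The condition main effect is a paired test on each person's mean difference.
- If 0.5 is the SD of the person-level hypoxia-sham difference, the SD of the mean difference is √(0.5² + 2/10) = 0.67. The noncentrality is 0.5 × √19 / 0.67 = 3.25, and power is about 87%.
- If 0.5 applies to each condition separately, the SD is √(2 × 0.5² + 2/10) = 0.84. The noncentrality is 2.60, and power is about 70%.

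The one-way F has 67–72% (51–55% with Greenhouse-Geisser) over the same two definitions. Repeat runs moved these figures by up to about three points.

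**Effect size.** On 20 cells with n = 19 the degrees of freedom are 19 and 19 × 18 = 342. With no effect of any kind (F about 1), partial eta squared is 19 / (19 + 342) = 0.05, close to the plan's medium. With the 0.3 shared trend and no hypoxia effect, the expected effect sum of squares is 19 + 19 × 20 × 0.3² = 53.2. Partial eta squared is then about 53.2 / (53.2 + 342) = 0.13, close to the plan's large.

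**The case against.** The strongest reply is that section 14.2 may intend something else. Section 10 includes a two-night home SpO2 recording at screening and a further CGM wear after visit 5. One summary per wear would give three levels: hypoxia, sham and the extra recording. Sphericity and post-hoc tests then have a role, and gated LSD does protect three means; in simulation the error was about 0.05. This reading is possible. But section 14.2 does not state it, and it drops the comparison across time that the section asks for.

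Second, the size depends on assumptions. The trend, the number of time levels and the residual structure are not in the documents, and the plan's own Greenhouse-Geisser step lowers the false-rejection rates. With no trend the gate holds the LSD error at or below about 5%. This stands, and is why the results are given as ranges with and without the correction.

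Third, the reach is limited. A hypoxia-sham difference in SpO2 is expected and serves largely as a check on exposure, so error control matters little there. The trial also calls itself a pilot. Both are fair, but the plan still uses P < 0.05 as a gate, and CGM glucose remains a secondary outcome that may shape the next trial.

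A reader might go further and infer that the plan cannot isolate a hypoxia-sham difference at all. The documents do not support that: a two-level analysis of summaries would isolate it, and matched-time LSD pairs do compare hypoxia with sham, though without error control.

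**Conclusion.** The point holds as a defect of specification in a secondary analysis. Section 14.2 names a one-factor model for two-factor data and leaves the levels open. On the readings its wording favours, a significant F does not specifically test hypoxia against sham, and LSD is not protected once a shared time trend opens the gate.

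With 10 time levels and 19 completers, the false-rejection rate of F runs from the nominal level or below with no trend to 90–96% at a trend SD of 0.3. The chance of a false same-night LSD difference runs from 1–5% to 38–39%, and is lower with fewer time levels. The power loss ranges from small to substantial, depending on how person-by-condition variation is defined and whether Greenhouse-Geisser is applied.

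Two stronger inferences should be resisted. The upper figures are not predictions for this trial, because no document gives the size of any drift. Nor does the point touch the primary outcome: section 14.2 assigns the OGTT glucose AUC to paired t-tests or Wilcoxon tests.

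**What to change.** In section 14.2:

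1. State the time levels to be analysed for SpO2 and for CGM glucose (for example nightly or daily means), and say whether the screening SpO2 nights and the CGM wear after visit 5 enter this model.
2. Replace the one-way ANOVA with a two-factor within-person model: condition, time, condition × time and period, with participant as a random effect. For the main question, a paired contrast of each person's hypoxia and sham means is equivalent with complete data and no period term.
3. Name the condition main effect as the planned test and the interaction as secondary.
4. Replace LSD with multiplicity-adjusted (e.g. Holm) hypoxia-minus-sham contrasts at matched times.
5. Report the hypoxia-sham difference with its confidence interval, and tie any partial eta squared to the condition term.

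This is a wording change that needs no new data or visits. The cost is slightly lower power for individual-night contrasts.
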